**\*Please enter the Short Title you would like to use to reference the study:**

Vivo SBIR

\* This field allows you to enter an abbreviated version of the Study Title to quickly identify this study.

## Add Study Organization(s):

**List Study Organizations associated with this protocol:**

Primary Dept?	Department Name		
	DUHS - Center for Study of Aging		
	DUHS - Medicine - Geriatrics		
	DUHS - Medicine-Endocrinology and Metabolism		

**OnCore**

**Please select the Library for your Protocol:**

This field is used in OnCore. Determines the Reference Lists, Forms, Protocol Annotations, Notifications, and Signoffs available for the protocol. Protocols that require reporting to the NCI (National Cancer Institute), must select the Oncology library.

Oncology  
 Non-Oncology

**Protocol Application Type**

**Select the type of protocol you are creating:**

Please see additional criteria and information in the policy titled "Reliance on the IRB of Another Institution, Organization, or an Independent IRB" on the [IRB web site](#).

Regular Study Application - Most common. The IRB will determine if the study is eligible for expedited review or requires full board review upon submission.  
 Application for Exemption from IRB Review - Includes Exempt, Not Human Subject Research, & Not Research.  
 External IRB Application - Any study using an external IRB as the IRB-of-Record.  
 Trainee Research While Away from Duke - Research conducted by medical students overseen by the Office of Curriculum & other student/trainee research away from Duke.  
 Individual Patient Expanded Access, Including Emergency Use - Use of an investigational product under expanded access, including emergency use of an investigational drug or biologic or emergency use of an unapproved device.

**Conflict of Interest**

**Are any key personnel an inventor of any of the drugs, devices or technologies used in this research?**

Yes  No

**Do any key personnel have a conflict of interest management plan issued by DOSI-COI related to this research?**

Yes  No

**Please give the name(s) of the relevant personnel. Please ensure the relationship is disclosed in the consent form before submitting the protocol.**

[name]

## Oversight Organization Selection

### CRU (Clinical Research Unit) or Oversight Organization Selection:

Please select the CRU.

Medicine

The Clinical Research Unit that takes responsibility for this study.

- Please select **Medicine** as the CRU **only** if the PI is in one of these Divisions or Institutes: Endocrinology, Gastroenterology, General Internal Medicine, Geriatrics, Hematology, Infectious Diseases, Nephrology, Pulmonary, Rheumatology & Immunology, Center for Applied Genomics and Precision Medicine, Center for the Study of Aging and Human Development, Duke Molecular Physiology Institute.
- More information on CRUs can be found on the Duke Office of Clinical Research (DOCR) website, <http://doctr.som.duke.edu>
- Questions concerning CRU selection should be directed to [contact].
- For questions about the Campus Oversight Organization, please visit **Campus Oversight Organization**.

#### Indicate the Protocol source below:

The protocol source is the author of the protocol. If the protocol is a joint authorship between multiple sources, select the primary author.

An IRB fee may be assessed for all research that is supported by for-profit entities and requires full board review. For additional information, see the **IRB fees section of the IRB web site**

- PI initiated
- Commercial / Industry (for-profit entity) initiated
- Federal Government initiated
- Cooperative Group Initiated
- Foundation (non-profit group) initiated
- Other

#### Sponsor and Funding Source

#### Add all funding sources for this study:

View Details	Sponsor Name	Sponsor Type	Contract Type:	Project Number	Award Number
	National Institutes of Health (NIH)	Externally Peer-Reviewed	Subcontract		
Sponsor Name:		National Institutes of Health (NIH)			
Sponsor Type:		Externally Peer-Reviewed			
Sponsor Role:		Funding			
Grant/Contract Number:		R44-AG076087-01			
Project Period:		From:01/01/2022 to:12/31/2024			
Is Institution the Primary Grant Holder:		No			
if No, then who is the Primary Grantee?		Vivo			
Contract Type:		Subcontract			
Project Number:					
Award Number:					
Grant Title:					
PI Name: (If PI is not the same as identified on the study.)					

Explain Any Significant Discrepancy:

**Is this a federally funded study?**

Yes  No

**Does this study have any of the following?**

- Industry sponsored protocol
- Industry funded Duke protocol
- Industry funded sub-contract from another institution
- Industry provided drug/device/biologic
- SBIR/STTR funded protocol

Yes  No

This study will require ORC review to ensure correct injury language is added to consent forms. Have you already received an email from ORC containing the appropriate language?

Yes  
 No  
 Not Applicable

**ORC Language Pending**

You can continue completing the application and submit it for review. You will need to incorporate the changes and upload the ORC or ORA email later via a Modification/Stipulation request. If you have any questions about this process, you can contact your ORC or ORA Agreement Manager.

**As part of this study, will any samples or PHI be transferred to/from Duke to/from anyone other than the Sponsor, a Sponsor subcontractor, or a Funding Source?**

Yes  No

**Is the Department of Defense (DOD) a funding source?**

Yes  No

**For Federally funded studies:**

**Is your funding subject to, and does it comply with, the funding agency's policy for data sharing?**

Yes  No

**Check all that apply:**

NIH Genome Sharing - dbGaP  
 NIH Genome Sharing - GWAS  
 NIH Genome Sharing - NCI databases  
 NIH Genome Sharing - other  
 Non-NIH Genomic  
 General Data Sharing

**Enter the Grant Number or Other Federal Agency Proposal or Application Number:**

**Note:** The Federal Funding Agency ID Number is the Sponsor's grant number assigned to your project and available on your Notice of Award (example: R01HL012345).

**If known, enter the SPS (Sponsored Projects System) number if applicable:**

26622

**In the Initial Submission Packet, attach the following:**

- (1) The entire grant, or an explanation of why a grant is not needed.
- (2) NIH institutional Certificate form related to data sharing (if applicable).

**Have you successfully synced your protocol to OnCore by clicking the 'Sync Data Over API' button at the top of this page?**

Please verify that the protocol has been created in OnCore before submitting this application for PI Signoff.

Yes, I synced my protocol to OnCore and verified it was successfully sent by logging into OnCore.

I may have forgotten! I'll click it again right now, just to be sure, and verify it was successfully sent by logging into OnCore.

**Mobile Devices and Software**

**Does this study involve the use of a software or a mobile application?**

Yes  No

**Please describe the following:**

- The developer of the mobile app and how the app will be obtained.
- What PHI will be collected via the app.
- Where the data will be stored and who will have access to it.

**Vivo:** Vivo, based in Atlanta, GA, is a technology platform that uses Zoom to support the premiere live and interactive online strength training program designed specifically for adults 55 and older. Vivo's corporate headquarters are at [name]. Vivo makes use of the Microsoft 365 cloud platform to provide the infrastructure to manage a remotely distributed workforce. Vivo trainers and staff are currently across the country in Georgia, South Carolina, North Carolina, New Jersey and California, and have the ability to be anywhere across the globe.

**Research Electronic Data Capture (REDCap) system (Vanderbilt/NIH)**

All participant data will be archived in a REDCap database. REDCap offers a mobile app; however, the mobile app will not be used for this study.

**List all software, including third party (non-Duke) and mobile apps, that will be utilized for ascertainment, recruitment, or conduct of the research/project: (eg, MaestroCare, DEDUCE):**

MaestroCare will be used for ascertainment and recruitment  
 Zoom will be used for conduct of the research project (see above)  
 REDCap will be used for storage of participant data (see above)  
 Duke Box will be used for storage of study documents

## Multi-site Research

### Is this a multi-site study?

Yes  No

## Research Abstract

Please type your Research Abstract here:

The Research Abstract should summarize the main points of your study in one paragraph. The following guidelines may help you:

1. Purpose and objective (1-2 sentences)
2. Study activities and population group (2-4 sentences)
3. Data analysis and risk/safety issues (1-2 sentences)

Aim: Evaluate the acceptability, feasibility, and fidelity of current Vivo prototype in sedentary older adults with prediabetes

This will be a 12-week single arm feasibility study using the currently available Vivo prototype. After informed consent and baseline assessments, 24 individuals will be enrolled in cohorts of 5-6 people. Each cohort will meet virtually twice a week with their small group and certified trainer for 45 minutes.

Participants will be men and women,  $\geq 60$  years old, sedentary, with prediabetes and low function. All participants will complete a pre- and post-intervention virtual physical function assessment, 3-day food record, height, weight, waist circumference, and social support, self-efficacy, and psychosocial functioning questionnaires. At 12-weeks, semi-structured interviews will be conducted to assess acceptability, usability and satisfaction.

In this single-arm feasibility study with pre- and post assessment (baseline and 12 weeks) we will use descriptive statistics to summarize the distribution of the covariates and dependent variables, and student t-tests to compare pre- and post-outcomes. These analyses are designed to support the feasibility of executing the fully powered randomized trial in Phase II. Table 2 summarizes all outcome measures. Qualitative interviews will be used to explore concepts related to barriers, acceptability, and retention of the health behaviors.

## Research Summary

### State your primary study objectives

Evaluate the acceptability, feasibility, and fidelity of current Vivo prototype in sedentary older adults with prediabetes.

### State your secondary study objectives

Access feasibility of intervention delivery.

### Please select your research summary form:

Standard Research Summary Template

This is the regular (generic) research summary template which is required for all regular applications (unless your protocol fits under the other research summary templates in this category). Use of these instructions is helpful for ensuring that the research summary contains all necessary elements.

## Standard Research Summary

### Purpose of the Study

- Objectives & hypotheses to be tested

Evaluate the acceptability, feasibility, and fidelity of current Vivo prototype in sedentary older adults with prediabetes

1: Assess a) attendance, benefits and barriers/facilitators of participation; b) ease of use; and c) overall satisfaction.

2: Assess trainer fidelity.

## Background & Significance

- Should support the scientific aims of the research

Most older adults experience a 30% loss in muscle mass between ages 50–70, resulting in increased risk of injury and even death, all of which can be prevented and managed with improved resistance training. Sarcopenia is the progressive loss of muscle mass and strength that is inevitable with aging; however, resistance training is the most effective strategy for improving both muscle mass and function and managing sarcopenia. With age, lean muscle mass naturally declines from about 50% of total body weight in young adults to about 25% at 75–80 yrs. The progressive deterioration of muscle quantity and quality leads to slower movement, a decline in strength and power, and increased risk for falls. Every 11 seconds, an older adult is treated for a fall in the emergency room; every 19 minutes, an older adult dies from a fall.

Because age-related muscle loss is reversible, a technology platform designed to support and guide users through resistance training represents a novel product despite the crowded digital fitness market. Decades of research have shown that resistance training is a feasible and effective modality to improve physical function, muscle quality (mass and strength), insulin sensitivity, cognitive function, quality of life and well-being, reduce the risk for falls, and prolong independent living and aging in place. Resistance training is highly effective in reversing age-related muscle loss in older adults with and without comorbidities. Studies of resistance training recommend that it is characterized by periodization and progression, i.e., 1) tailored to the individual, 2) regular periods of work that include multiple sets of multi-joint exercises for each major muscle group at intensities of 70-85% of 1 rep maximum, and 3) done at least twice a week. Despite the well-established benefits of resistance training, most older adults don't meet this exercise threshold: only 19.3% of adults aged 65-74, and <15% of older adults aged  $\geq 75$  report meeting the federal guideline of performing moderate/high intensity muscle strengthening involving all major muscle groups on  $\geq 2$  days per week.

Why don't older adults participate in strength training exercise? Older adults report not participating in resistance training due to lack of age appropriate programs, fear of a gym setting, poor access to a gym, joint and other kinds of pain, and lack of social support. These barriers have been compounded as a result of COVID-19, wherein older adults are encouraged to socially isolate, leading to even less physical activity.

Especially relevant today during the Covid pandemic, population-based studies show that socially isolated and lonely older adults have a 59% higher risk of physical and mental health decline. Vivo addresses these major barriers to carrying out strength training with the social support and ease of use factors leading to our product's popularity during the pandemic last year (The New York Times, December 14, 2020). Vivo trainers deliver strength training instruction and coaching through an interactive online training session incorporating social support and social engagement. Vivo is a monthly membership based online resistance training program where small groups (families, friends, couples) work with a trainer for 45 minutes 2-3 times/week on building strength, flexibility, balance, and cognitive skills. Typically, there is a maximum of 6 participants per group. Classes are structured and designed to measure progress and provide custom feedback to all users.

Other than the live classroom experience via Zoom the current Vivo prototype does not have interactive dashboard capability. Feedback about performance and resistance training outcomes are all recorded manually and discussed over Zoom with the trainer at each session. To date since the onset of the pandemic in March 2020, 92 people have participated in Vivo (age range 44-93). We conduct baseline and 8-week functional assessments on all participants. Even with the technological limitations we found excellent proof of concept in our small pilot study of 34 older adults (74% women; mean age 70.9 y; range 60-84y) after 8 weeks of participating in Vivo with a certified trainer (average of 12 hours of training per person). We observed:

- +25.8% improvement in upper body strength as measured by the 30 second arm curl test
- +25.9% improvement in lower body strength as measured by the 30 second chair stand test
- +28% improvement in endurance as measured by the 2-minute knee raise test

## Design & Procedures

- Describe the study, providing detail regarding the study intervention (drug, device, physical procedures, manipulation of the subject or the subject's environment, etc.). Discuss justifications for placebo control, discontinuation or delay of standard therapies, and washout periods if applicable. Identify procedures, tests and interventions performed exclusively for research purposes or more

frequently than standard of care. Include alternative therapies, concurrent therapies discontinued per protocol, risk benefit ratio, and use of tissue/specimens. Discuss monitoring during washout periods if applicable. Include brief description of follow-up, if any.

This will be a 12-week single arm feasibility study using the currently available Vivo prototype to assess 1) adherence and retention, 2) acceptability and satisfaction with Vivo, 3) technology useability (i.e., Zoom, email), and 4) change in physical function in sedentary older adults with prediabetes and lower function.

**Remote Consent:** The study informational session is done one-on-one via a scheduled ZOOM meeting appointment with study staff. The secured REDCap platform will be used to obtain the participants' electronic consent (eConsent).

After informed consent and baseline assessments, 30 individuals will be enrolled in cohorts of 5-6 people.

Physical Function, Activity, and Diet Outcomes (baseline and week 12)	
Physical measurements	Height, weight, and waist circumference
30-second chair stands to quantify lower body strength	Number of full stands that can be completed in 30 seconds with arms folded across chest
Short Physical Performance Battery to quantify balance, lower extremity strength	Balance (side-by-side, semi-tandem, tandem), strength (time to complete 5 chair stands).
Gait speed tests	Number of seconds required to walk 4 meters
2-minute step test to measure aerobic endurance	Number of full steps completed in 2 minutes, raising each knee to a point midway between the patella (kneecap) and iliac crest (top hip bone)
8-ft Up and Go to assess agility/dynamic balance	Number of seconds required to get up from a seated position, walk 8 feet (2.44 m), turn, and return to seated position
30-second arm curl to quantify upper body strength	Number of arm curls completed in 30 seconds
Social Support and Self-efficacy	
Social Support	Perceived social support: "The people I spend most of my time with now encourage me in physical fitness activities" using a rating scale 1: strongly disagree and 5: strongly agree  Social Support within Vivo: "I have received support and encouragement from other [Vivo] participants to continue participating in this program?" 5-point scale of agreement
Self-efficacy	Five item question to determine beliefs in capability when faced with potential barriers, "Over the next three months, I am confident I can attend Vivo when ... (I am tired, in a bad mood, feel I don't have time, am on vacation, it's raining or snowing) with a 7-point scale of agreement 
Psychosocial Functioning	

Quality of Life; Mood; Depression; Stress, and satisfaction with life

Short Form Health Survey 36 (SF-36), Profile of mood state (POMS), Center for Epidemiologic Studies Depression Scale (CES-D), Perceived Stress Scale (PSS), Satisfaction with Life (SWL)

Each participant will receive a welcome kit that includes resistance bands to use during class along with written instructions about the assessments, and a tape measure.

Each cohort will meet virtually twice a week with their small group and certified trainer for 45 minutes.

All participants will complete a pre- and post-intervention virtual physical function assessment, 3-day food record, height, weight, waist circumference, and social support, self-efficacy, and psychosocial functioning questionnaires.

At 12-weeks, semi-structured interviews will be conducted to assess acceptability, usability and satisfaction.

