**Where will the consent process occur?**

Participants will be consented virtually via Zoom or Webex and will sign the consent form electronically using Redcap.

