**c) Whenever appropriate, the subjects will be provided with additional pertinent information after participation:**

N/A, if subject chooses not to participate and subsequently consent to the study, all PHI data of the potential subject will be destroyed at the end of the recruitment period.

**d) If this research activity relates to research involving deception, explain how subjects will be provided with additional pertinent information after study participation and what information will be provided. Otherwise indicate "not applicable":**

N/A

**e) The use or disclosure of protected health information involves no more than minimal risk to the privacy of individuals, based on, at least, the presence of the following elements (e1. and e2.)**

**Demonstrate that the use or disclosure of PHI involves no more than minimal risk to the privacy of subjects by describing the plans requested below:**

**e1) An adequate plan to protect the identifiers from improper use and disclosure. Describe the plan (how protection will be accomplished) and indicate where the PHI will be stored and who will have access:**

PHI will be stored in a folder in Duke Box accessible only to study staff.

**e2) An adequate plan to destroy the identifiers at the earliest opportunity consistent with conduct of the research, unless there is a health or research justification for retaining the identifiers or such retention is otherwise required by law.**

**Describe the plan (how and when identifiers will be destroyed and by whom). If there is a health or research justification for retaining the identifiers or such retention is otherwise required by law, provide the reason to retain identifiers:**

For individuals who decline or do not qualify for the study based on information provided before informed consent is obtained, all personally-identifiable PHI in the screening log will be shredded/destroyed and the individual's names and contact information will be removed from our subject database. PHI for individuals who do not qualify or who do not consent to participate will be destroyed at the end of the recruitment period. For individuals who do qualify for the study, we will obtain written consent to use their PHI.

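### Technology usability and feasibility are assessed only in people who have already got through three remote steps, with no planned count of eligible people lost to technology on the way

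*Combined protocol and SAP*

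**What the plan says.** Design & Procedures gives the study four things to assess, the third being "3) technology useability (i.e., Zoom, email". Ease of use is also listed under Purpose of the Study, feasibility is part of the primary objective, and feasibility of delivering the intervention is the secondary objective.

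The same section sets the route into the study:

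- Information session: "The study informational session is done one-on-one via a scheduled ZOOM meeting appointment with study staff".
- Consent: "The secured REDCap platform will be used to obtain the participants' electronic consent (eConsent"). The Consent Process section agrees: "Participants will be consented virtually via Zoom or Webex and will sign the consent form electronically using Redcap". No paper or in-person route is described.
- Baseline: "All participants will complete a pre- and post-intervention virtual physical function assessment".
- Enrolment: "After informed consent and baseline assessments, 30 individuals will be enrolled in cohorts of 5-6 people". The Research Abstract instead says "24 individuals will be enrolled in cohorts of 5-6 people".

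Usability is to be explored in a semi-structured interview at 12 weeks. WiFi in the exercise space is an inclusion criterion; ability to use Zoom or to sign electronically is not. The first exclusion criterion covers anyone who cannot complete the physical function assessment, whatever the cause.

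The outcome table in Design & Procedures and the outcome list in Data Analysis & Statistical Considerations contain no screening, consent or technology-loss measure. On records, item e2 of the waiver criteria says "PHI for individuals who do not qualify or who do not consent to participate will be destroyed at the end of the recruitment period".

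**The concern.** The product under test is a live class on Zoom. The Background says that the current prototype has no interactive dashboard beyond it. Using Zoom to admit people and then asking those admitted whether Zoom is usable selects, in part, on the outcome. A person who meets every listed inclusion criterion, has WiFi, but cannot join the session, sign electronically or be tested by video is a feasibility failure for this product, and would not appear in any planned result.

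The analyses are said to support the feasibility of running the randomised Phase II trial. If entry to that trial is also remote, the same losses will determine how many people must be approached to fill it. Reasons that staff do not record at the time may not be recoverable once the identifiable log is gone.

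**Working it through.** **No figure to reproduce.** The documents give no usability rate, feasibility threshold, sample-size derivation or expected technology loss. The check is therefore of order and denominators, followed by an illustration on assumed inputs.

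**Order and capture of losses**

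| Step | Remote technology needed | Loss counted in a planned outcome or analysis? |
|---|---|---|
| Phone screen | None; internet access is recorded | No |
| Information session | Zoom | No |
| Consent | Zoom or Webex, REDCap signature | No |
| Baseline function assessment | Virtual | No; a technical failure can be recorded as the first exclusion criterion |
| Enrolment | – | This is where the 30 (or 24) are counted |
| Classes, weeks 1 to 12 | Zoom | Yes, through attendance, adherence and retention |
| Week-12 interview | Not stated | Usability asked here; whether early leavers are interviewed is not stated |

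**Size of the possible overstatement.** Let N otherwise eligible people start the remote steps, f be the share lost to technology before enrolment, and s the success rate among the enrolled. Then N(1 − f) enrol and sN(1 − f) succeed. Counting those lost to technology as not successful, the rate among starters is s(1 − f), so the enrolled-only rate is too high by s − s(1 − f) = s × f.

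Both inputs are assumptions: s of 80% or 90%, f from 0% to 30%.

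| f | Rate among starters, s = 80% | Overstatement | Rate among starters, s = 90% | Overstatement |
|---|---|---|---|---|
| 0% | 80% | 0 | 90% | 0 |
| 5% | 76% | 4.0 points | 85.5% | 4.5 points |
| 10% | 72% | 8.0 points | 81% | 9.0 points |
| 20% | 64% | 16 points | 72% | 18 points |
| 30% | 56% | 24 points | 63% | 27 points |

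For scale, s = 90% with 30 enrolled is 27/30, with an exact 95% interval of 73.5% to 97.9%. An overstatement of 4.5 or 9 points leaves a value (85.5% or 81%) inside that interval; at 18 or 27 points the value (72% or 63%) falls below it. The interval describes sampling error only and says nothing about people never enrolled.

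**What the consent cap can and cannot show.** The form allows at most 34 consents. That leaves 34 − 30 = 4 people (4/34 = 11.8%) or 34 − 24 = 10 people (10/34 = 29.4%) between consent and enrolment, depending on which enrolment figure is right. The cap is an upper limit, not an expected number. It does not bound losses at the Zoom session or the electronic signature, which come before or at consent.

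**The case against.** Usability among people able to connect is a legitimate target: the product is a Zoom class and WiFi is an open entry criterion. For that group the entry route adds no bias. Technology trouble after enrolment can still show, since participants must join twice a week for 12 weeks, and attendance, barriers, ease of use and retention are all assessed. Trainer fidelity is not directly affected. No go/no-go rule is stated that an inflated figure could tip. All of this stands, and it limits the point to the wider eligible population.

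Three stronger readings are tempting and are not supported.

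- *That nobody is counted before enrolment, or that reasons for loss are discarded.* A phone screen, a screening log and a limit on consents all exist. The destruction clause concerns identifiable information collected before consent. The documents are silent on de-identified counts and reasons. The gap is that none is planned or reported.
- *That the result is biased upward by a known amount.* A reader might set 27 finishers over 30 enrolled (90%) against 27 over 34 consented (79.4%) and call the 10.6-point difference the bias. The 27 is not in the documents, 34 is a cap, 30 conflicts with 24, and the comparison treats all four losses as technology losses. Eligibility depends on chair-stand performance, and the phone-screen items listed in the waiver request include no such test, so some people may be found ineligible on function after consent.
- *That retention should be headlined on everyone who consented.* That would count people found ineligible on function as retention failures and push retention down for a reason unrelated to the programme.

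**Conclusion.** The point holds in limited form. As written, the plan would assess Zoom usability and participant-level feasibility only in people who have already managed a Zoom session, an electronic signature and a virtual assessment, and would not report those who could not. For the wider eligible population with WiFi, the error from this source is zero or upward. Its size is s × f, and f is unknown: nothing if no one is lost to technology, about 4 to 9 points at 5% to 10% loss, and 16 to 27 points at 20% to 30% loss. These figures rest on assumed s of 80% to 90% and on counting technology losses as not successful. They show how the result depends on f and do not estimate the bias. The change is worth making because ease of use and feasibility are the study's own aims and the missing information is cheap to collect at the time.

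**What to change.** In Design & Procedures and in Data Analysis & Statistical Considerations:

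1. State that at each step from the phone screen onward (Zoom session joined, eConsent signed, virtual baseline completed, first class joined) staff will record a de-identified count, a reason for loss (technology, function or otherwise ineligible, time, other) and any need for staff technical help.
2. State that these counts and reasons are kept after the identifiable log is destroyed and are reported as a feasibility outcome.
3. Separate technical from physical failure when the function-assessment exclusion is applied.
4. Keep retention among the enrolled as the retention figure. Beside it, show the proportion lost to technology among people who were otherwise eligible or not found ineligible.
5. State that week-12 usability applies to people able to connect, and say whether early leavers are interviewed.
6. Reconcile the enrolment figures: 24 in the Research Abstract, 30 in Design & Procedures and in Subject Recruitment and Compensation.

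The cost is a few extra data fields, completed by staff who already run these sessions, and possibly a less favourable feasibility figure.
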